17.2.2.1. Analysis of Secondary Pharmacokinetic Endpoints

For analysis of secondary PK endpoints, refer to Section 19 for details.

17.2.3. SECONDARY PHARMACODYNAMIC ENDPOINTS

Reduction of peripheral eosinophil count from Baseline (Day 1) to EOS visit (Day 127)

Whole blood ex vivo induced IFN-y levels

Document: \\ieedc-vnasc01\biosdata\AnaptysBio\ANB020\CYA74392\Biostatistics\Documentation\SAP\Final\20181218 Version Number:

Author:

Version Date: 18Dec2018

Template No: CS_TP_BS016 Revision 4 Reference: CS_WI_BS005

Effective Date: 01Apr2016

AnaptysBio Inc PROTOCOL ANB020-004 Page 27 of 46

17.2.3.1. Analysis of Secondary Pharmacodynamic Endpoints

For analysis of secondary PD endpoints, refer to Section 20 for details.

17.3. EXPLORATORY ENDPOINTS

17.3.1. EXPLORATORY EFFICACY ENDPOINTS

Clinical scores for ACQ-7 (Screening, Day 1, 8, 22, 36, 64, 85, 106, and EOS), PGIC (throughout the study), and CGIC (Day 2, 8, 22, 36, 64, 85, 106, and EOS)

Patient diary data of asthma symptoms, change in standard of care treatment, and rescue medication (SABA) usage (collected throughout the study)

Reduction of IgE levels from Baseline (Day 1) to the EOS visit (Day 127)

17.3.1.1. Analysis of Exploratory Endpoints

The FAS will be used for the exploratory efficacy analysis.

Total ACQ-7 will be calculated as sum of all individual scores for each patient at each visit.

Symptoms will be scored on a scale of 0 to 6 with 6 being the worst case. ACQ-7 will be missing if any individual score is missing.

The actual and change from baseline for ACQ, PGIC, CGIC, and IgE levels will be summarized using appropriate descriptive statistics by treatment groups at all time points where assessment is done. Change from baseline will be evaluated where possible.

PGIC and CGIC scores will be collected during the study for an overall response to the treatment where a score of 1 implies "Very much improved" and a score of 7 implies "Very much worse".

Applicable diary assessments, e.g. frequency of asthma symptoms (wheezing, cough, shortness of breath, chest tightness, etc.) experienced during the week, number of patients receiving rescue medication, and number of patients who have change in SOC treatment will be summarized using appropriate descriptive statistics.

Applicable exploratory endpoints analyses will be performed same as secondary efficacy analyses. Clinical Global Impression of Change Scale (CGIC Scores) and Patient Global Impression of Change (Summary of PGIC Scores) will be analysed using Cochran–Mantel–Haenszel test at each visit by row-

Document: \\dieedc-vnasc01\biosdata\AnaptysBio\ANB020\CYA74392\Biostatistics\Documentation\SAP\Final\20181218 \\
Author: \quad \text{Version Number: 1.0}

Version Number: 1.0 Version Date: 18Dec2018

Reference: CS_WI_BS005

Template No: CS_TP_BS016 Revision 4

Effective Date: 01Apr2016

mean-score-difference test using ridit scores to compare ANB020 vs placebo. Patient-wise data listings will be provided.

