#### Daily Recording

- Number of puffs that the patient needed to use their rescue (SABA) medication during the day.

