Table 14 2 4 2 Asthma Symptoms (Patient Diary) – Full Analysis Set

	r rounna o j mp	oms (rationt blary) ran	Timely DID Det		
Characteristic	Visit	Statistics	ANB020 (N=XX)	Placebo (N=XX)	Total (N=XX)
Number of Patients needed to use Rescue Inhaler	<visits></visits>	n (%)	xx (xx x)	xx (xx x)	xx (xx x)
Number of Patients needed to use Rescue Medication	<visits></visits>	n (%)	xx (xx x)	xx (xx x)	xx (xx x)
Number of Patients Experiencing Wheezing	<visits></visits>	n (%)	xx (xx x)	xx (xx x)	xx (xx x)
Cough	<visits></visits>	n (%)	xx (xx x)	xx (xx x)	xx (xx x)
Shortness of Breath	<visits></visits>	n (%)	xx (xx x)	xx (xx x)	xx (xx x)
Chest Tightness	<visits></visits>	n (%)	xx (xx x)	xx (xx x)	xx (xx x)
Others	<visits></visits>	n (%)	xx (xx x)	xx (xx x)	xx (xx x)
Number of Patients who Changed Any of their Prescribed Long Term Controller Medicine	<visits></visits>	n (%)	xx (xx x)	xx (xx x)	xx (xx x)
Number of Patients Rating the Study Treatment as <categories></categories>	<visits></visits>	n (%)	xx (xx x)	xx (xx x)	xx (xx x)
Number of Patients who Rating the Level of Satisfaction With the Side Effects Related to the Study Treatment as <categories></categories>	<visits></visits>	n (%)	xx (xx x)	xx (xx x)	xx (xx x)

Document: \\ieedc-vnasc01\\biosdata\\AnaptysBio\\ANB020\\CYA74392\\Biostatistics\\Documentation\\SAP\\Final\\20181218 Author:

Version Number: 1.0 Version Date: 18Dec2018

CONFIDENTIAL

Table Shells

Clinical Study Report ANB020-004 - Original

AnaptysBio Inc. PROTOCOL ANB020-004 Page 30 of 51

Table 14 2 4 2 Asthma Symptoms (Patient Diary) – Full Analysis Set

Characteristic Visit Statistics ANB020 Placebo Total (N=XX) (N=XX)

Source: Listing 16.2.6.4

Note:

- N is the number of patients within each treatment group under Full Analysis Set

- Baseline will be last non-missing measurement taken prior to reference start date (including unscheduled assessments or retests)

Percentages are based on number of patients within each treatment group under Full Analysis Set (N). Programming Note: Continue this table for all available visits.

Table 14 2 5 1

Clinical Global Impression of Change Scale (CGIC Scores) - Full Analysis Set

Source: Listing 16 2 6 5

Table 14 2 6 1
Exploratory Endpoint: Reduction from Baseline in IgE levels(Unit) on Day 127/ET – Full Analysis Set

	ANB020	Placebo
Statistic	(N=XX)	(N=XX)
1	xx	XX
LS Mean	XXX.XX	XXX.XX
SE of LS Mean	XX.XXX	XX.XXX
95% CI	[xxx.xx, xxx.xx]	[xxx.xx, xxx.xx]
LS Mean Difference (ANB020 – Placebo)	XX.XX	

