- Total ACQ has been calculated as sum of all individual scores for each patient at each visit. ACQ will be missing if any individual score is missing.

Document: Author: \\lieedc-vnasc01\biosdata\AnaptysBio\ANB020\CYA74392\Biostatistics\Documentation\SAP\Final\20181218

Version Number: Version Date: 1.0 18Dec2018

29 June 2020

AnaptysBio Inc. PROTOCOL ANB020-004 Page 26 of 41

Listing 16.2.6.4 Patient Diary - Full Analysis Set

Patient No./ Treatment	Age/ Gender	Visit	Date of First Diary Entry/ Date of Last Diary Entry/ Study Days	Need to Use Rescue Inhaler	If Yes, Total Number of Puffs/ Total Number of Days the Rescue inhaler Used	Description of the Change Related to Asthma ^[a]	Experiencing any Symptom/ If Others, Specify	Change in any of the Prescribed Medicine/ Specify	Rate of Study Treatment	Level of Satisfaction with the Side Effects Related to Study Treatment
XXX/ XXX/	32/ Male	Screening	DDMMMYYYY/ DDMMMYYYY/ xx/xx	No	-	2	Other/ xxxx	No	Good	Good
		Baseline	DDMMMYYYY/ DDMMMYYYY/ xx/xx	Yes	xx/ xx	2	Cough	Yes/ xxxx	Fair	Good
		<visits></visits>								

Note:

- Study day is calculated for both first and last diary entry date.
 - If Date of assessment ≥ Reference Start Date then Study Day= (Date of assessment Reference start date) +1, else Study Day= Date of assessment Reference start date.
- [a]: 1=Very much improved, 2= Much improved, 3=Minimally improved, 4=No changes, 5=Minimally worse, 6=Much worse, 7=Very much worse.

Document: Author:

Version Number: Version Date:

1.0 18Dec2018

126

AnaptysBio Inc.
PROTOCOL ANB020-004
Page 27 of 41

Listing 16.2.6.5 Clinical Global Impression of Change Scale - Full Analysis Set

Patient No./ Treatment	Age/ Gender	Visit	CGIC Performed/ If No, Specify Reason	Date of Assessment/ Study Day	Description of the Change in Patient's Overall Asthma Symptom	Any Asthma Exacerbations Occurred Since the Past Week	Type of cercerbation
XXX/ XXX/	32/ Male	Day 2	No/ xxxx	-	-	-	-
7000	Water	Day 8	Yes	DDMMMYYYY/ xx	4	Yes	Inpatient hospitalization due to asthma (>24hrs)
		<visits></visits>					
XXX/ XXX/	31/ Female	Day 2	Yes	DDMMMYYYY/ xx	2	No	-
XXX	1 cmarc	<visits></visits>					

Note:

- CGIC: Clinical Global Impression of Change Scale.
- [a]: 1=Very much improved, 2= Much improved, 3=Minimally improved, 4=No changes, 5=Minimally worse, 6=Much worse, 7=Very much worse

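### SABA puffs are recorded daily and listed as totals, but the only planned by-arm summary of rescue use is any/no use per visit interval, which is insensitive and not comparable across visits

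*SAP*

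**What the plan says.** The effect on rescue use is an exploratory objective in both documents. SAP 17.3.1 lists the endpoint as diary data that include "rescue medication (SABA) usage (collected throughout the study").

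Protocol 6.1.4 has patients enter a count each day: "Number of puffs that the patient needed to use their rescue (SABA) medication during the day". Cards are handed out from screening onwards and returned at the next clinic visit.

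For analysis, SAP 17.3.1.1 gives examples of diary summaries. The one for rescue use is the "number of patients receiving rescue medication". The shell of Table 14.2.4.2 follows suit, with n (%) by visit for "Number of Patients needed to use Rescue Inhaler" and a matching row for rescue medication. Its footnote reads "Percentages are based on number of patients within each treatment group under Full Analysis Set (N").

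The counts themselves appear patient by patient in Listing 16.2.6.4, in the column "If Yes, Total Number of Puffs/ Total Number of Days the Rescue inhaler Used", next to the first and last diary entry dates.

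A general sentence in SAP 17.3.1.1 adds: "Applicable exploratory endpoints analyses will be performed same as secondary efficacy analyses". Protocol 9.5 has a similar rule and counts applicable diary assessments among the exploratory variables. Neither document says which diary items are applicable. The table shells contain model-based tables for ACQ and IgE, and none for puffs.

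**The concern.** A daily count is reduced to a yes/no per visit interval before the arms are compared. A patient who goes from six puffs a day to one puff a week stays in the same category. The exploratory objective asks about usage, and the planned table can register only patients who become, or stop being, completely reliever-free for a whole interval.

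Two features of the table add to this. The visit intervals are unequal, and the chance of at least one use grows with interval length, so the percentage can move between visits with no change in behaviour. The fixed FAS denominator also puts a patient with no diary among the non-users, so missing data look like benefit.

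At stake is an early clinical signal in a small proof-of-concept trial. The primary endpoint and the safety conclusions are not affected.

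**Working it through.** The plan states no figure to reproduce. The sample size is not power-based, and no SABA rate, SD or target difference is given. The use rates below are therefore assumptions, shown as a range.

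**Inputs from the documents.** Clinic visits fall on Days 1, 2, 8, 22, 36, 64, 85, 106 and 127 (Protocol 4.1), with 12 patients per arm (Protocol 6.2.2). Tests of treatment effects are two-sided at 0.05 (SAP 6.5).

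**Step 1: interval lengths.** 2−1 = 1, 8−2 = 6, 22−8 = 14, 36−22 = 14, 64−36 = 28, then 21, 21 and 21 days, ignoring visit windows.

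**Step 2: chance of any use, same daily probability p in every patient, independent days.** P(any) = 1 − (1 − p)^d.

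| p (assumed) | 1 day | 6 days | 14 days | 21 days | 28 days |
|---|---|---|---|---|---|
| 0.05 | 5% | 27% | 51% | 66% | 76% |
| 0.1 | 10% | 47% | 77% | 89% | 95% |
| 0.2 | 20% | 74% | 96% | 99% | 99.8% |

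For example, 1 − 0.8^14 = 0.956 and 1 − 0.8^28 = 0.998. Reading along a row shows the comparability problem. With constant behaviour at p = 0.1, the table would show 10% at Day 2, 47% at Day 8, 77% at Days 22 and 36, 95% at Day 64 and 89% thereafter.

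**Step 3: patients who differ in use.** Let p follow a beta distribution with mean m, a = mk and b = (1 − m)k. Then P(any) = 1 − B(a, b + d)/B(a, b). With k = 1 to 2 (smaller k means wider differences), any use over 14 days is 28–38% at m = 0.1, 58–71% at m = 0.25 and 85–93% at m = 0.5. Over 28 days it is 33–45%, 65–79% and 89–97%. Differences between patients can remove the ceiling.

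**Step 4: what a contrast would need.** With 12/12 in one arm, the two-sided Fisher p against x/12 is 2·C(12,x)/C(24,12+x) for these values.
- x = 8: 2 × 495/10626 = 0.093.
- x = 7: 2 × 792/42504 = 0.037.

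Five of 12 patients would have to use no reliever at all during the interval.

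**Step 5: illustration with daily use halved, 21-day interval, 12 per arm.** Any use is assessed by exact Fisher power. Share of days with use is assessed by a t-test in 3,000 simulated trials.

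| Assumed mean daily use | Any use, by arm | Power, any use | Power, share of days |
|---|---|---|---|
| 0.5 to 0.25, same in all | 100% vs 99.8% | about 0% | >99% |
| 0.3 to 0.15, same in all | 99.9% vs 96.7% | about 0% | 98% |
| 0.5 to 0.25, k = 2 | 95.5% vs 76.1% | 8% | 55% |
| 0.3 to 0.15, k = 2 | 82.5% vs 56.7% | 15% | 30% |
| 0.5 to 0.25, k = 1 | 87.8% vs 62.0% | 16% | 41% |
| 0.3 to 0.15, k = 1 | 69.2% vs 43.2% | 16% | 23% |

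Over all halving scenarios tried (6 to 28 days, mean daily use 0.05 to 0.7), Fisher power for any use ran from about 0% to 17%.

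**Step 6: denominator.** If 9 of 12 patients return a diary and all 9 used SABA, the shell gives 9/12 = 75%. Among patients with data it is 9/9 = 100%. The general rule in SAP Section 6 excludes missing values unless otherwise stated, and this table's footnote states otherwise.

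**The case against.** The strongest reply has four parts.

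1. Puffs are not lost. Listing 16.2.6.4 shows total puffs and days of use, and ACQ item 6 grades puffs per day. A reader might infer that rescue use is reported only as yes/no, but the listing contradicts that. What stands is that no by-arm summary of puffs is specified. ACQ item 6 feeds only the ACQ-7 total and an item-level listing, and the later file note adds ACQ-5, which leaves item 6 out.

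2. The list in SAP 17.3.1.1 is illustrative, and the general rule there and in Protocol 9.5 could cover puffs. This is fair, and it narrows the gap. But the word applicable is undefined, no puff variable is named, and the shells show where the rule was applied: ACQ and IgE, not puffs.

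3. A reader might infer that any use will sit near 100% in both arms. The documents do not support this. They give no SABA rate and no minimum-use entry criterion; the only rescue-related criterion is an exacerbation needing rescue medication in the previous 12 months. The ceiling needs frequent use in nearly all patients over the longer intervals. It fails at Day 2, can fail at Day 8, and fails if some patients seldom use SABA.

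4. A reader might infer that the planned analysis has almost no power and cannot show an effect. No test of the any/no counts is specified: SAP 17.3.1.1 asks for descriptive statistics and the shell has no p-value row. The power figures only illustrate how little the measure responds, and they rest on assumed rates. The trial is not sized on power for any endpoint.

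**Conclusion.** The point holds as a minor improvement to an exploratory endpoint. Three parts follow from the documents without assuming any rate of use. Intensity is left out of the only specified by-arm summary. The percentages are not comparable across intervals of 1 to 28 days. The FAS denominator treats a missing diary as no use.

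The insensitivity at 12 per arm is also firm in one respect: 12/12 against 8/12 would not reach p<0.05. How close the table would come to a ceiling is uncertain, from 51% to 96% over 14 days for p between 0.05 and 0.2, and lower with wide differences between patients. In all six 21-day scenarios share of days with use was more sensitive than any use, but the margin ranged from 23% against 16% to more than 99% against about 0%. The direction is reliable and the size is not.

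**What to change.** In Table 14.2.4.2, for each visit interval and among patients with diary data, add:
- mean puffs per day (total puffs divided by diary days completed);
- percent rescue-free days;
- change in each from the 7–14-day screening diary, defined explicitly as the diary baseline;
- the number of patients contributing diary data.

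Compare puffs per day between arms with the baseline-adjusted model the SAP already uses for the secondary efficacy endpoints, on a log-type scale if the counts are skewed. Report differences with 95% CIs and label them exploratory. State in SAP 17.3.1.1 that puffs per day is an applicable endpoint. Keep any/no use as a descriptive row, with patients who returned a diary as the denominator. The one-day interval to Day 2 is best left descriptive.

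The cost is one derived variable and one extra table, with no new data or visits. The drawback is a choice of transformation for skewed counts that may include many zeros, to be fixed before unblinding. If the database holds only the totals shown in the listing, completed diary days would have to be approximated from the first and last entry dates, and the SAP should say so.

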17.3.2. EXPLORATORY PHARMACODYNAMICS ENDPOINTS

Circulating cytokines including, but not limited to interleukin IL-4, IL-5, , IL-13, IL-33, and sST2 at day 1, 2, 8, 22, 36, 64, and EOS.

17.3.2.1. Analysis of Exploratory Pharmacodynamic Endpoints

For analysis of exploratory PD endpoints, refer to Section 20 for details.

18. SAFETY OUTCOMES

Safety analyses will be based on the SAF.

The following are the safety and tolerability endpoints:

- o Assessment of Adverse Events (AEs)/ Serious Adverse Events (SAEs)
- o Physical examination
- o Vital signs
- o Clinical safety laboratory tests
- o Electrocardiograms
- o Number of asthma exacerbations
- o Assessment of immunogenicity (ADA status)

There will be no statistical comparisons between the treatment groups for safety data.

18.1. ADVERSE EVENTS

AEs will be coded using MedDRA version 19.1.

Treatment emergent adverse events (TEAEs) are defined as AEs that started or worsened in severity on or after the date and time of the study drug infusion.

Non-treatment emergent adverse event (Non-TEAE) will be defined as any AE that started on or after the date of informed consent and before the administration of study drug.

AEs with missing start dates will be considered treatment-emergent. AEs with missing stop dates or

Document: \\ieedc-vnasc01\biosdata\AnaptysBio\ANB020\CYA74392\Biostatistics\Documentation\SAP\Final\20181218 \\
Author: \quad \text{Version Number:} \quad 1.0

Version Date: 18Dec2018

Template No: CS_TP_BS016 Revision 4 Reference: CS_WI_BS005

Effective Date: 01Apr2016

AnaptysBio, ANB020 CONFIDENTIAL

IND 126765, SN 0035

Clinical Study Report ANB020-004 - Original

AnaptysBio Inc PROTOCOL ANB020-004 Page 29 of 46

IQVIA STATISTICAL ANALYSIS PLAN

with stop dates after the end of the study date will be considered to have been ongoing at the end of the study.

The severity of AEs will be characterized as "mild, moderate, severe" according to the following definitions:

Mild events are usually transient and do not interfere with the patient's daily activities

Moderate events introduce a low level of inconvenience or concern to the patient and may interfere with daily activities

Severe events interrupt the patient's usual daily activity

Missing severity will be assumed to be the worst severity case i.e. 'severe'; however, in the listing, it will be displayed as missing.

The causal relationship between the study drug and the AE will be characterized as "Unrelated, Unlikely, Possible, Probable, and Unknown (unable to judge)".

The summaries will be presented as "Related" versus "Not Related".

Categories "Unrelated" and "Unlikely" will be mapped to "Not Related", while the categories "Possible", "Probable" and "Unknown" will be mapped to "Related".

Missing relationship will be assumed to be the worst severity case i.e. 'Related; however, in the listing, it will be displayed as missing.

An overview of adverse event along with the number and percentage of patients experiencing TEAEs, for each treatment group will be provided.

If patient has multiple TEAEs by severity and/or multiple relationship with study drug, worst case severity and the worst-case relationship to the study drug will used for overview tabulation.

For TEAE by final outcome, if a patient has multiple TEAEs with different outcomes, worst case will be considered, where 'Fatal' being the worst.

For Action Taken with the Drug, patient can be counted in more than one categories.

The following summary tables will be provided by SOC and PT for each treatment group and overall:

- Number of patients with at least one TEAE o
- Number of patients with at least one serious TEAE 0

Document:

\\ieedc-vnasc01\biosdata\AnaptysBio\ANB020\CYA74392\Biostatistics\Documentation\SAP\Final\20181218

Version Number: 1.0

Reference: CS_WI_BS005

Version Date: 18Dec2018

Template No: CS_TP_BS016 Revision 4

Effective Date: 01Apr2016

Author:

Clinical Study Report ANB020-004 - Original

AnaptysBio Inc PROTOCOL ANB020-004 Page 30 of 46

- Number of patients with at least one TEAE by severity 0
- Number of patients with at least one TEAE by relationship to study drug 0
- Number of patients with at least one TEAE leading to permanent discontinuation of study 0 drug
- Number of patients with at least one TEAE leading to interruption of study drug 0
- Number of patients with at least one TEAE leading to patient withdrawal from study 0
- Number of patients with at least one TEAE leading to death 0
- Number of patients with non-TEAE 0

If an AE occurs more than once, the patient will be counted only once per SOC and once per PT within each SOC. If a patient reports a TEAE more than once within a SOC/PT, the AE with the worst-case severity will be used in the corresponding severity summaries and the worst-case relationship to the study drug will be used in the corresponding relationship summaries.

Percentages will be calculated relative to the total number of patients in the SAF. The summaries will be sorted by descending frequencies of SOC and descending frequencies of PT with in SOC.

Listings will be provided for TEAEs, Serious TEAEs, TEAEs leading to discontinuation from study or from IP, and TEAEs leading to death for the SAF.

